3. STUDY DESIGN

3.1 STUDY DESIGN

Part A of this study is a global, randomized, double-blind, placebo-controlled, parallel-group, multi-center Phase III study with a [REDACTED] screening period, a 48-week treatment period, and safety follow-up visits [REDACTED] and [REDACTED] after last dose.

A total of approximately 230 patients with FSHD will be randomized 1:1 to receive 15 mg orally of losmapimod (n~115) or placebo (n~115) tablets twice daily (BID) with food for 48 weeks (see Figure 1 of protocol for a design schematic). Approximately 210 patients with genetically confirmed FSHD1 and 20 patients with genetically confirmed FSHD2 will be randomized.

- For the FSHD1 cohort, randomization will be stratified by the number of FSHD repeats (1- 3 versus 4-9) to ensure that an equal number of patients are allocated to treatment and placebo within each FSHD repeat number category.
- The FSHD2 cohort will be separately randomized to ensure that an equal number of patients will be allocated to treatment and placebo. Randomization will not be stratified for the FSHD2 cohort.

During the treatment period in Part A, patients will be asked to attend the study clinic at each scheduled visit (see Appendix B below).

Scheduled visits may be split over 2 days if required, with a maximum of 5 business days between visits. Unscheduled visits may be performed if clinically indicated.

See Section 4 of the protocol for inclusion and exclusion criteria.

For patients who do not continue in the Open Label extension, safety follow-ups of [REDACTED] and [REDACTED] are implemented once a patient takes the last dose of study drug.

3.2 RATIONALE OF STUDY DESIGN

See Section 3.2 of the protocol for full details of the rationale for the study design.

4. TIMING OF PLANNED ANALYSES

4.1 INTERIM ANALYSES

No formal interim analysis is planned during Part A. Safety and a limited set of statistics summarizing efficacy will be presented at periodic Independent Data Monitoring Committee (IDMC) meetings, without unblinding of the sponsor and vendor teams involved with the analyses described in this SAP.

4.2 FINAL ANALYSIS

The planned final analysis will be performed following the end of Part A of the study, and when all required database cleaning activities for Part A data have been completed, and the database has been declared clean and locked by data management. This is after all patients who have decided to continue into the OLE have had their Week 48 visit; and after all other patients have completed their safety follow-up visit.

5. SAMPLE SIZE CONSIDERATIONS

The target population for this clinical trial is patients with FSHD1 and FSHD2. The clinical trial will reflect the current epidemiologic information about FSHD, with patients with FSHD1 making up approximately 95% of the study population and the other 5% being people living with FSHD2.

Assuming the within-group standard deviation (SD) of change is 0.08, a sample size of 210 patients with FSHD1 (105 patients per group) will be needed to provide at least 95% power with a 2-sided t-test at 0.05 significance level to detect a difference of 0.05 between losmapimod and placebo for the primary endpoint. An additional approximately 20 patients with FSHD2 will be recruited. The primary analysis will include patients with FSHD1 and FSHD2. Premature withdrawal and missing data are discussed in 9.1.

For the secondary efficacy endpoints of change from baseline in WB longitudinal composite MFI of B Muscles and PGIC at Week 48, assuming the within-group SDs are 0.72 and 1.0 respectively, a sample size of 210 patients with FSHD1 will provide at least 95% power with a 2-sided t-test at 0.025 significance level to detect a difference of 0.5 and 0.6 respectively between losmapimod and placebo.

For the secondary efficacy endpoint of relative change from baseline in average shoulder abductor strength at Week 48, assuming the within-group SD is 46, a sample size of 210 patients with FSHD1 will provide at least 75% power with a 2-sided Wilcoxon rank-sum test at 0.025 significance level to detect a difference of 20.2 between losmapimod and placebo.

In the above calculations, the assumed treatment differences and SDs are based on results from an ongoing Phase 2 study, Study FIS-002-2019 (ReDUX4). It is also assumed that 10% of the study population has missing Week 48 data. All power calculations were performed using the POWER Procedure of SAS[®] Version 9.4.

6. ANALYSIS POPULATIONS

6.1 FULL ANALYSIS SET

The FAS will consist of all patients with FSHD1 or FSHD2 who are randomized and receive at least 1 dose of study drug in the placebo-controlled treatment period. All analyses using the FAS will group patients according to randomized treatment, regardless of which treatment the patient actually received.

6.2 SAFETY ANALYSIS SET

The safety analysis set will consist of all patients who receive any study drug. All analyses using the safety analysis set will group patients according to treatment actually received, regardless of which treatment the patient was randomized to. If a patient receives both losmapimod and placebo, the patient will be assigned to the losmapimod group in the safety analysis set.

6.3 PHARMACOKINETIC ANALYSIS SET

The pharmacokinetic (PK) analysis set will consist of all patients who receive at least 1 dose of losmapimod and have non-missing PK data for losmapimod.

7. PROTOCOL DEVIATIONS

Protocol deviations are defined as any change, divergence, or departure from the study design in the CSP.

Significant deviations are protocol deviations that affect important efficacy and safety assessments (as applicable), the safety or mental integrity of a patient, or the scientific value of the trial/project.

8. GENERAL CONSIDERATIONS FOR DATA ANALYSES

8.1 STANDARD SUMMARY STATISTICS

Continuous data will be summarized using descriptive statistics (n, mean, standard deviation (SD), standard error (SE), median, first quartile, third quartile, minimum, and maximum). Categorical data will be summarized using the count and percentage in each category. When count data are presented, in cases where the count is zero, the percentage will not be displayed, in order to draw attention to the non-zero counts. A row denoted 'Missing' will be included in count tabulations where specified on the shells to account for dropouts and missing values. The denominator for all percentages will usually be the number of patients in that treatment group within the analysis set of interest (i.e., including patients with missing data). Exceptions to this are when binary or categorical variables are derived from changes from baseline, where the denominator is all patients within the analysis set of interest with non-missing baseline. . Percentages will be displayed to 1 decimal place, except in the case of 100% which will be presented with no decimal places.

For the summary statistics of all numerical variables unless otherwise specified, minimum and maximum will be displayed to the same level of precision as reported in the raw data. Mean, median, quartiles, 95% CI, SD and SE will be displayed to one level of precision greater than the data collected. P-values will be rounded to four decimal places. A p-value below 0.0001 will be reported as "<0.0001." A p-value above 0.9999 will be reported as ">0.9999". Data will be presented in summary tables, listings, and figures. Where appropriate, an estimation approach will be taken, and point estimates and confidence intervals (CIs) of interest will be constructed. Patients will be identified in the listings by patient identification number. Summary statistics will be presented by treatment arm and/or overall (if required). In the case where the number of patients included in an analysis is 0, no statistics will be presented; if only one patient is included, then only n, and mean will be presented.

All analyses will be conducted using SAS® Version 9.4 or higher.

8.2 STRATA AND COVARIATES

Patients will be randomly assigned at the baseline visit (Day 1) to receive losmapimod (active drug) or placebo using a 1:1 allocation ratio. Randomization will be stratified to ensure that treatment allocation is balanced across 3 strata based on FSHD repeat number category and FSHD type:

- FSHD 1, repeat numbers 1-3
- FSHD 1, repeat numbers 4-9
- FSHD 2

Inferential models will be adjusted for the above 3-level FSHD repeat number category (except subgroup analyses by FSHD Repeat Number Category). If the stratification category used at randomization is different from the correct category, the stratification category used in analyses will be the category used at randomization for the primary analyses of the primary endpoint and alpha-protected secondary endpoints (see 2.4.2), while the correct category will be applied in the sensitivity analyses of the primary endpoint and alpha-protected secondary endpoints, and the correct category will be applied in all other efficacy analyses. If the number of patients with non-missing data in any level of the FSHD repeat number category < 5 in either treatment group in any inferential analysis, the data from that level in both treatment groups will not be included in that inferential analysis. If such a situation occurs in at least 2 of the 3 levels, the inferential analysis will be performed on data from all patients without adjusting for the 3-level FSHD repeat number category. All inferential models will include a fixed effect for region: North America / Europe (except subgroup analyses by region). If the number of patients with non-missing data in either region < 5 in either treatment group in any inferential analysis, the inferential analysis will be performed on data from all patients without adjusting for region.

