9.1.5. Description of Subgroups to Be Analyzed

Any planned subgroup analyses will be described in the SAP for Part A. Subgroups will include a subgroup of patients with FSHD2 and subgroups of region, sex, and age.

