8.5 EXAMINATION OF SUBGROUPS

Subgroup analyses of the primary and secondary efficacy endpoints will be conducted. Subgroups to be analyzed are:

- Correct FSHD type 1 repeat categories 1-3; FSHD type 1 repeat categories 4- 9; FSHD type 2
- Baseline clinical severity score (Ricci score 2- 3 and 3.5- 4)
- Region (North America and Europe)
- Sex (Male and Female)
- Age (<45 years old and \geq 45 years old)
- Baseline weight (<77kg vs \geq 77kg)

The by-site analysis of the primary endpoint will also be performed.

Note: models will be fitted for all subgroups, but in the case of failure to converge due for example to small sample size, model results will not be presented.

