10.2 EFFICACY ANALYSES

Efficacy analyses are based on the FAS. The primary and secondary efficacy analyses will also be split by subgroup of the FAS.

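### SAP 8.2 deletes a single sparse FSHD stratum from both arms but keeps every patient when two strata or a region are sparse; at planned enrolment this affects the subgroup models, not the primary analysis

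*SAP*

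**What the plan says.** SAP 8.2 adjusts inferential models for a three-level category: FSHD1 with 1-3 repeats, FSHD1 with 4-9 repeats, and FSHD2. Only the subgroup analyses by that category omit the term. The section then sets three fallbacks, each triggered by fewer than five patients with non-missing data in either arm.

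- One sparse stratum: "the data from that level in both treatment groups will not be included in that inferential analysis".
- Two or three sparse strata: "If such a situation occurs in at least 2 of the 3 levels, the inferential analysis will be performed on data from all patients", with the stratum term dropped.
- A sparse region: "the inferential analysis will be performed on data from all patients without adjusting for region".

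On populations, SAP 6.1 says "The FAS will consist of all patients with FSHD1 or FSHD2 who are randomized and receive at least 1 dose of study drug". SAP 10.2 bases efficacy on that set and adds: "The primary and secondary efficacy analyses will also be split by subgroup of the FAS". SAP 8.5 says "Subgroup analyses of the primary and secondary efficacy endpoints will be conducted" and lists five two-level factors (Ricci score, region, sex, age, weight) besides the FSHD category. Protocol 9.1.5 names three of them: "Subgroups will include a subgroup of patients with FSHD2 and subgroups of region, sex, and age". On numbers, SAP 3.1 says "Approximately 210 patients with genetically confirmed FSHD1 and 20 patients with genetically confirmed FSHD2 will be randomized".

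**The concern.** The same trigger has opposite consequences. Patients are removed when sparsity is mild (one stratum) and retained when it is worse (two strata) or when it concerns region. The SAP does not say why.

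FSHD2 is planned at about 10 patients per arm, so any split into halves leaves about five per arm, right at the threshold. Whether FSHD2 stays in a given subgroup model is then largely chance. One half of a sex or age comparison may describe FSHD1 only while the other includes FSHD2. A reader of the subgroup results would take the two halves as a partition of the FAS, and they would not be one. The descriptive statistics by visit would still count the FSHD2 patients that the model beside them had dropped.

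**Working it through.** **The plan's own figures.** The documents give no probability for this rule. The nearest stated figure is primary power in SAP 5: SD 0.08, difference 0.05, 105 FSHD1 patients per arm, 10% missing, at least 95%. With 94 evaluable per arm the two-sided t-test has 98.9% power, so that statement holds. Power does not rest on the FSHD2 patients.

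**Inputs.** From the documents: the threshold of five; 20 FSHD2 patients randomised 1:1, so 10 per arm; 105 FSHD1 patients per arm; 10% missing at Week 48. Assumed, because not documented: *k* = 10, 15, 20 or 30 patients per arm with 1-3 repeats; a 50:50 subgroup split; missing rates other than 10%.

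**Formula.** Let *q* = subgroup share × (1 − missing rate). The chance that a stratum of *n* per arm has fewer than five in at least one arm is

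S(n, q) = 1 − [1 − BinomCDF(4; n, q)]².

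FSHD2 is deleted only if it is the one sparse stratum:

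P = S(10, q) × [1 − S(k, q)] × [1 − S(105 − k, q)].

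With q = 0.5, BinomCDF(4; 10, 0.5) = 0.377, so S(10, 0.5) = 1 − 0.623² = 0.612. For k = 10, P = 0.612 × 0.388 = 0.237. For k = 15, S(15, 0.5) = 0.115 and P = 0.612 × 0.885 = 0.541. The figures for two halves jointly come from simulating the same model (1,000,000 draws).

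| 1-3 repeats per arm (*k*) | 10 | 15 | 20 | 30 |
|---|---|---|---|---|
| No missing: FSHD2 deleted from a given half | 24% | 54% | 60% | 61% |
| No missing: from at least one half | 46% | 86% | 93% | 94% |
| No missing: from exactly one half | 44% | 64% | 65% | 66% |
| No missing: 1-3 repeat stratum deleted instead | 24% | 5% | 0.5% | 0% |
| 5% missing: given half / at least one | 22 / 42% | 57 / 88% | 67 / 97% | 69 / 98% |
| 10% missing: given half / at least one | 19 / 37% | 58 / 87% | 73 / 97% | 75 / 99% |

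A hand check at large *k*: with no missing data neither half loses FSHD2 only if both arms split 5/5, which has probability (252/1024)² = 0.061. At least one half therefore loses it with probability 94%.

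The 10% rows suit analyses of the Week 48 value alone, such as the Wilcoxon test. For an MMRM, counting anyone with a post-baseline value, the lower missing rates apply; SAP 8.2 does not say which count is meant. With unequal halves and no missing data, FSHD2 is deleted from a 40% subgroup with probability 12-86% and from a 60% subgroup with probability 21-30%. If all five two-level factors split evenly, the expected number of the ten halves losing FSHD2 is 10 × P = 2.4, 5.4, 6.0 or 6.1.

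**Effect on an estimate.** A deletion removes on average 8.75 of about 114-116 patients, or 7.6-7.7% of the half. Take the extreme case of no effect in FSHD2 and the full 0.05 in FSHD1. The shift is 0.077 × 0.05 = 0.0039, against an SE of 0.08 × √(2/57.5) = 0.0149, a ratio of 0.26. The SE rises by a factor 1/√(1 − 0.077) = 1.04.

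**Full-population analyses.** For the primary MMRM with 10 FSHD2 patients per arm, S(10, 0.98) = 2.5 × 10⁻⁸ and S(10, 0.95) = 5.5 × 10⁻⁶. With 8 per arm the values are 2.1 × 10⁻⁵ and 7.4 × 10⁻⁴. For a Week 48 analysis at 10 per arm and 10% missing, S is 0.03%.

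**The case against.** The rule is prespecified and removes a whole stratum from both arms, so the remaining comparison is still randomised. It causes no type I error problem, and the effect on an estimate is small. All of that stands.

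The asymmetry can also be read coherently. With one stratum removed, two usable strata remain to adjust for; with two removed, nothing would be left, so the SAP keeps everyone. That may be the reasoning, but it does not show that patients must be deleted in the first case.

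FSHD2 information is not lost altogether: FSHD2 has its own planned subgroup analysis, and the by-visit descriptive statistics retain these patients. SAP 8.2 can also be taken as a specific rule qualifying the general sentence in 10.2. Both points soften the conflict with the FAS description without giving a reason for one-sided exclusion.

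The figures lean on an undocumented stratum size and assumed splits, which is why ranges are shown. At *k* = 10 the 1-3 repeat stratum is as likely to be deleted as FSHD2, and both are sparse together with probability 0.612² = 37%, in which case everyone is kept. That FSHD2 is usually the stratum lost therefore depends on *k* being larger.

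Finally, pooling is not free. The contrast becomes 1-3 repeats against 4-9 repeats plus FSHD2, and a chance imbalance of FSHD2 between arms within a subgroup is no longer adjusted for. That cost is real but small beside excluding the patients.

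**Conclusion.** The concern holds as a minor, optional improvement. At the planned 20 FSHD2 patients its reach is the two-level subgroup models, which lie outside the alpha-controlled sequence in SAP 2.4.2. Under the stated assumptions it is more likely than not, for *k* of 15 or more, that one half of an even split excludes FSHD2 while the other includes it. The consequence is a mismatch in the population described, not a biased comparison.

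The primary analysis becomes exposed only if FSHD2 enrolment falls well short of 20. The documents leave some room for that: SAP 5 and Protocol 9.1.3 also put FSHD2 at 5% of the study, which is 11.5 of 230 or about six per arm, whereas 20/230 is 8.7%. At six per arm the trigger probability in the full population would be about 6% with 5% missing and 22% with 10% missing.

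**What to change.** Replace the deletion sentence in SAP 8.2 with wording such as:

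> When exactly one level of the FSHD category falls below five evaluable patients in an arm, it is combined, for adjustment or stratification only, with the FSHD1 4-9 repeats level (or with the FSHD1 1-3 repeats level when the 4-9 level is itself the sparse one). No patient is excluded.

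Keep the existing rule for two or more sparse levels. State that the same rule governs the stratified Wilcoxon tests (for example SAP 10.2.2.3) and the Cochran-Mantel-Haenszel tests (for example SAP 10.2.2.1).

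The cost is one SAP sentence and a small recoding of the stratum variable in sparse analyses, with no new data. The price is a slightly coarser adjustment in those analyses: when FSHD2 is the sparse level, 1-3 repeats is still separated from 4-9 repeats, with FSHD2 grouped with the latter.

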8.3 STANDARD COMPARISON METHODS

8.3.1 Primary and secondary endpoint analyses

Continuous endpoints with multiple post-baseline assessments will be analyzed using mixed-effects models for repeated measures (MMRM). Models will include terms for treatment group, visit,

treatment group by visit interaction, baseline value, baseline value by visit interaction, stratification category (FSHD repeat number category: FSHD 1, 1-3; FSHD 1, 4-9; FSHD 2; see 8.2), and region (North America, Europe). An unstructured covariance matrix will be used to model the correlations between repeated measurements within each patient. If the unstructured covariance matrix results in a lack of convergence, the first-order autoregressive covariance structure followed by the compound symmetric covariance structure will be used. The Kenward-Roger approximation will be used to estimate denominator degrees of freedom [2, 3]. Windowing (see 9.5.1) will be applied to ensure no more than one measurement per target visit window, per patient. Least-square (LS) mean, standard error, 2-sided 95% CI, and a 2-sided within-group p-value will be presented for each treatment group, at each visit. The difference in LS means between treatment groups (Losmapimod 15 mg BID – Placebo BID), the 2-sided 95% CI of the difference, and a 2-sided p-value will be presented at each visit.

In addition, certain continuous endpoints with multiple post-baseline assessments will be analyzed using a linear mixed-effects model (LME, see 10.2). In these models the response variable is the absolute measurement, at baseline and post-baseline assessments. Models will include terms for treatment group, time, treatment group by time interaction, FSHD repeat number category (FSHD 1, 1-3; FSHD 1, 4-9; FSHD 2; see 8.2), and region (North America, Europe). Intercept and time will be fitted as random effects. In this model, 'time' is time from first dose normalized over the treatment period of 48 weeks (335 days). It is derived as follows:

$$\text{Time} = (\text{Assessment/event date} - \text{Date of first dose}) / 335$$

[figure not shown]
The treatment effect will be assessed over the entire treatment period (i.e., 48 weeks) for each treatment group. Data to be included (scheduled and unscheduled) will be selected through windowing. An unstructured covariance matrix will be used to model the correlations between repeated measurements within each patient. If the unstructured covariance matrix results in a lack of convergence, the first-order autoregressive covariance structure followed by the compound symmetric covariance structure will be used. LS mean, SE and 2-sided 95% CI for the slope and intercept, and a 2-sided p-value for the slope, will be presented for each treatment group. The difference in LS mean slopes between treatment groups (Losmapimod 15 mg BID – Placebo BID), the 2-sided 95% CI of the difference, and a 2-sided p-value will be presented. In addition, the average percentage change per year (annualized percentage change) will be presented for each treatment group. This is derived as $[(\text{slope}/\text{baseline}) * (365/335) * 100]$, where baseline is the LS mean intercept, slope is the LS mean slope and 335 is the planned duration of treatment with study drug in days minus 1. The difference in average percentage change per year between treatment groups (Losmapimod 15 mg BID – Placebo BID) will also be presented.

Least squares means derived from the MMRMs will be plotted over time for both treatment groups with error bars showing standard errors. Annualized percentage changes estimated from LMEs will be presented as line charts.

For all MMRMs and LMEs fitted, model assumptions will be checked by examining plots of residuals. Given the sample size of the study and the nature of the variables investigated, the central limit theorem (CLT) is highly likely to guarantee that the analysis of means is appropriate. However, if the

distributions of the data strongly imply the CLT isn't appropriate, the analysis may rely on nonparametric methods or transformations of the data.

In the case that a model does not converge under any of the three covariance structures, analysis will consist of descriptive statistics only.

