2.4.2 Multiple testing strategy

To control the overall type I error rate, the primary endpoint and secondary efficacy endpoints will be tested in sequence as follows:

1. The primary endpoint will be tested at 2-sided significance level $\alpha=0.05$.
2. If a statistically significant result is obtained for the primary endpoint (test 1), change from baseline in WB longitudinal composite MFI in B muscles at Week 48 and relative change from baseline in average shoulder abductor strength by hand-held quantitative dynamometry at Week 48 will be tested using the Bonferroni procedure, i.e., each will be tested at 2-sided $\alpha = 0.025$ (test 2).
 - If both tests are significant, a statistically significant result is obtained from test 2. The remaining significance level from test 2 = 0.05.
 - If only one of the 2 tests is significant, a statistically significant result is obtained from test 2. The remaining significance level from test 2 = 0.025.
 - If neither test is significant, a statistically significant result is not obtained from test 2.
3. If a statistically significant result is obtained from test 2, PGIC at Week 48 will be tested at the remaining significance level from test 2 (test 3).
4. If a statistically significant result is obtained from test 3, change from baseline in Neuro-QoL-UE at Week 48 will be tested at the remaining significance level from test 3, which is equal to the remaining significance level from test 2.

In recognition of the complexities of this rare disease and the novelty of this research field, in case the result of the primary analysis (MMRM) of the primary endpoint is on the boundary of statistical significance, but at least one of the following is true:

- results from most sensitivity analyses are nominally significant,
- result of PGIC at Week 48 is nominally significant,
- result of Change from baseline in WB longitudinal composite MFI in B muscles at Week 48 is nominally significant,

AND

- results from most of the remaining secondary and exploratory efficacy endpoints are directionally favorable to losmapimod,

the totality of evidence will be utilized to support the decision making.

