9.3.3 Efficacy derivations

9.3.3.1 Primary endpoint

Change from baseline in average total RSA Q1-Q5 with 500 g wrist weight at Week 48, where the average is applied over both arms.

The RWS (total RSA Q1-Q5) measurements required for the analysis of the primary endpoint are those assessed at baseline and at weeks 4, 12, 24, 36 and 48, on both the dominant and non-dominant arms. At each visit the RWS for each arm (Left and Right) is the sum of the 5 RSA measurements: Q1+Q2+Q3+Q4+Q5, where the weight used is 500g. The average total RSA is the average of the two totals:

Average = Mean of (Total for Left Arm with 500g weight, Total for Right Arm with 500g weight)

Change from baseline is derived as specified in 9.2. above.

Note: the average over both arms per visit needs to be calculated before computing changes from baseline.

If an arm is not tested for RWS, and the reason code is W='Weakness related', then the RWS for that arm should be imputed as 0.

Because the RWS data are used in the primary endpoint analysis for this study, Fulcrum or its designated vendor will perform additional cleaning of these data. Fulcrum or its designated vendor will use the following criterion to identify potentially invalid data points: post-baseline data points that show a change (increase or decrease) >50% from the previous result on total RSA Q1-Q5. Records meeting this criterion will be sent to the RWS vendor for further investigation. After blind review, the RWS vendor will communicate to Fulcrum or its designated vendor any records that are deemed invalid because of problems with the software and should therefore not be included in the analysis. These rare sessions, if any, will be flagged by the RWS vendor, and their associated results, including total RSA Q1-Q5, total RSA Q1-Q4, sum of Q1 and Q3, and all 5 individual quadrants, will be removed from the RWS analysis (also see 9.3.3.3).

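### If the unstructured MMRM fails for a five-visit endpoint and the variance grows over visits, the AR(1) and CS fallbacks understate the Week 48 standard error

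*SAP*

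**What the plan says.** The primary analysis is an MMRM of change from baseline in average total RSA. The measurements used "are those assessed at baseline and at weeks 4, 12, 24, 36 and 48", so there are five post-baseline visits. SAP 8.3.1 specifies an unstructured covariance with Kenward-Roger degrees of freedom. If that fit does not converge, "the first-order autoregressive covariance structure followed by the compound symmetric covariance structure will be used". Protocol 9.1.1 and 9.1.6.3 repeat the rule. If none of the three structures converges, SAP 8.3.1 reports descriptive statistics only.

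No heterogeneous structure and no empirical standard error is named for this step. The documents do not say whether the fallbacks are homogeneous. SAP 8.1 has all analyses run in SAS, where plain AR(1) and CS each carry one common variance. This review adopts that reading.

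PGIC (SAP 10.2.2.1) and Neuro-QoL-UE (10.2.2.4) use the same MMRM at the same five visits. MFI (10.2.2.2) uses it with two post-baseline visits, Weeks 24 and 48. Shoulder abductor strength (10.2.2.3) is tested by a Wilcoxon test and is not affected.

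**The concern.** A homogeneous structure gives Week 48 a variance averaged over all visits. If patients spread apart over time, the early visits pull that average below the true Week 48 variance, and the standard error of the Week 48 treatment difference is too small. Kenward-Roger adjusts for estimating the covariance parameters of the chosen structure. It does not repair a wrong structure.

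Growth is plausible here. The companion linear mixed model in SAP 8.3.1 gives each patient a random slope, and if slopes differ, the variance of change rises with time. Section 1 of the protocol describes FSHD as progressive, with RSA declining over years.

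The primary test opens the testing sequence in SAP 2.4.2, so an inflated error there would pass to the secondary endpoints. A fallback is needed only when the first choice fails, and it should hold its error rate then.

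**Working it through.** **Inputs from the documents.**
- Test level: "The primary endpoint will be tested at 2-sided significance level" 0.05 (SAP 2.4.2).
- SD: "Assuming the within-group standard deviation (SD) of change is 0.08" (SAP 5). This is the only SD given for this endpoint.
- Effect: "to detect a difference of 0.05 between losmapimod and placebo for the primary endpoint", with 105 FSHD1 patients per group (SAP 5).
- Missing data: "It is also assumed that 10% of the study population has missing Week 48 data" (SAP 5).
- Total size: "A total of approximately 230 patients with FSHD will be randomized 1:1" (SAP 3.1), so about 115 per arm.

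**The plan's own power figure.** Evaluable per arm: 105 × 0.9 = 94.5. SE = 0.08 × √(2/94.5) = 0.01164. Power = Φ(0.05/0.01164 − 1.960) = Φ(2.336) = 0.990. The claim of at least 95% is met with room to spare.

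**Effect of a homogeneous fallback.** In large samples with complete data, let r be the model SE divided by the true SE at Week 48. Then r = (pooled SD)/(Week 48 SD), and

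type I error = 2 × [1 − Φ(1.960 × r)].

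For CS, the pooled variance is the mean of the five visit variances. For AR(1), it is the value that best fits the assumed covariance and comes out almost the same.

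*Worked case, assumed SDs 0.05, 0.0575, 0.065, 0.0725, 0.08 (CS).* Mean variance = (0.002500 + 0.003306 + 0.004225 + 0.005256 + 0.006400)/5 = 0.0043375, so the pooled SD is 0.0659. r = 0.0659/0.08 = 0.823. Type I error = 2 × [1 − Φ(1.613)] = 0.107.

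**Range over assumed patterns.** The Week 48 SD is fixed at 0.08; linear patterns rise or fall in equal steps per visit. The simulation used 115 per arm under the null, monotone dropout reaching 10% at Week 48, REML, and 2,500 to 4,000 replicates. It used t with 200 df in place of Kenward-Roger and omitted region and stratum.

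| SD pattern, Week 4 to Week 48 | r, AR(1) / CS | Type I error, AR(1) / CS | Simulated, AR(1) / CS |
|---|---|---|---|
| 0.10 falling to 0.08 | 1.129 / 1.128 | 0.027 / 0.027 | 0.030 / 0.032 |
| constant 0.08 | 1.000 / 1.000 | 0.050 / 0.050 | 0.050 / 0.048 |
| 0.07 to 0.08 | 0.939 / 0.939 | 0.066 / 0.066 | 0.062 / 0.063 |
| 0.06 to 0.08 | 0.880 / 0.879 | 0.084 / 0.085 | 0.099 / 0.106 and 0.079 / 0.081 (two runs) |
| half the Week 48 variance from random slopes | 0.837 / 0.830 | 0.101 / 0.104 | 0.097 / 0.102 |
| 0.05 to 0.08 | 0.825 / 0.823 | 0.106 / 0.107 | 0.102 / 0.102 |
| 0.04 to 0.08 | 0.774 / 0.771 | 0.129 / 0.131 | 0.131 / 0.136 |
| variance proportional to time | 0.725 / 0.719 | 0.155 / 0.159 | 0.166 / 0.172 |

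**When the error doubles.** A type I error of 0.10 needs r ≤ 1.645/1.960 = 0.839, that is, a pooled variance at or below 0.839² = 0.704 of the Week 48 variance. With linear growth, the Week 4 SD must be about 0.05 or lower.

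**MFI.** With two visits, an unstructured matrix has two variances and one correlation. So do heterogeneous Toeplitz, heterogeneous AR(1) and heterogeneous CS; all four are the same model. Homogeneous AR(1) and CS also coincide. If the Week 24 SD is 0.85 of the Week 48 SD (assumed), r = √[(0.85² + 1)/2] = 0.928. At MFI's level of 0.025, type I error is 2 × [1 − Φ(2.241 × 0.928)] = 0.038.

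**The case against.** The strongest reply is that the fallback will hardly ever be used for the primary test. Five visits need 15 covariance parameters, and about 230 patients should support them. This stands: the unconditional type I error of the primary test moves little.

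Second, growing variance is an assumption. The annualized RSA declines quoted in Section 1 of the protocol (1.63% to 2.74%) are small, so measurement noise that is roughly constant over visits may make up much of the 0.08. This also stands as a limit on size. It does not show that the variance is constant, because a small mean decline says nothing about how much slopes differ between patients.

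Third, the plan has other checks. The residual plots in SAP 8.3.1 lead to a change of method only if the distributions cast doubt on the central limit theorem, which does not clearly cover unequal visit variances. The rank analysis in SAP 10.2.1.2 (Sensitivity Analysis 5) does not rely on this covariance, but it is supportive and does not replace the primary test.

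A reader might infer three stronger points that the documents do not support:
- *The error reaches MFI and the subgroups in the same way.* For MFI, the three-parameter matrix is unlikely to fail and the inflation is smaller. Subgroups lie outside the testing sequence, and SAP 8.5 withholds results on failure to converge. The FSHD2 subgroup, about 20 patients, is still where a fallback fit is most likely to be used, because three structures are tried before a model counts as failed.
- *AR(1) is wrong because visits are unequally spaced.* Only the gap from Week 4 to Week 12 differs from 12 weeks, and CS, which ignores spacing, gives nearly the same error.
- *The plan names homogeneous structures.* It does not; that is the usual reading. If heterogeneous versions were meant, the text should say so.

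**Conclusion.** The point holds in conditional form and is a minor one. If the unstructured fit fails for RSA, PGIC or Neuro-QoL-UE, and the variance grows over visits, the listed fallbacks understate the Week 48 standard error.

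The size depends on visit SDs that the documents do not give. For RSA at the 0.05 level, the range shown runs from about 0.03 with falling SD, through 0.05 with constant SD, to about 0.16 with variance proportional to time (0.17 in simulation). No variance pattern was available for PGIC or Neuro-QoL-UE, so no figure is claimed for them.

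A reader might conclude that the primary test's type I error is doubled. The documents do not support that as a fact. Doubling needs both a failed unstructured fit and a pooled variance no more than about 70% of the Week 48 variance.

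**What to change.** In SAP 8.3.1 and Protocol 9.1.1 and 9.1.6.3, replace the MMRM fallback order with heterogeneous Toeplitz, then heterogeneous AR(1), then heterogeneous CS, each with Kenward-Roger. For five visits these have 9, 6 and 6 parameters, against 15 for unstructured, and each keeps a separate Week 48 variance. If a homogeneous structure is still needed as a last resort, use empirical (sandwich) standard errors in place of Kenward-Roger, and name a compatible df method. For MFI, only this last step applies, because the heterogeneous structures would refit the model that failed. Update the SAP sentence that moves to descriptive statistics after three structures.

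The cost is a few sentences in each document and a somewhat larger Week 48 standard error when a fallback is used. In the 0.05 to 0.08 case it is 1/0.823 = 1.21 times the homogeneous one. The planned power is not at risk from this, since the 99% above already uses the Week 48 SD of 0.08. That the new order restores an error rate of about 0.05 follows from r = 1; it was not simulated, and convergence of the new structures was not examined.
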